6.4 Follow-up Assessments

6.4.1 Follow-up for All Subjects

Follow-up visits will occur in-office at 3, 6, 12, 18, and 24-months (± 30 days) after permanent system implementation is complete. Any reprogramming must be performed only after all patient questionnaires have been administered.

The following data will be collected at each visit:

- Occupational status
- Pain condition-related medication usage (e.g., analgesics, opioids, anti-convulsants, anti-depressants)
- NRS
- PROMIS-29
- PCS
- PVAQ
- Patient satisfaction
- Physician satisfaction
- Device programming (if applicable)
- Device-related adverse events (if applicable)
- Serious adverse events (if applicable)
- Device deficiency (if applicable)
- Withdrawal (if applicable)
- Death (if applicable)

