6.5.1 PROMIS-29

The PROMIS-29 is a 29-item profile instrument that covers 7 health domains (depression, anxiety, physical function, pain interference, fatigue, sleep disturbance, and social function) with 4 questions each. The final item is an 11-point pain intensity numerical rating scale (NRS). Subjects should read each item and check the one box that most closely represents their response.

Each item is scored on a scale from 1-5 with total scores for each domain ranging from 4-20. Greater scores represent more of whatever concept is being measured (e.g., depression or physical function). Version 2.1 of the PROMIS-29 will be used for this study and scoring tables have been provided in the measure manual. Raw domain scores are converted to t-scores with a mean of 50 and a standard deviation of 10. The t-scores were validated on a sample from the general population and all items must be answered to utilize the scoring tables. If forms are incomplete, the Health Measures Scoring Service (https://www.assessmentcenter.net/ac_scoringservice) can be used to generate appropriate t-scores.

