2.3 Endpoint Analysis

2.3.1 Endpoints

[figure not shown]
The following endpoints will be successively evaluated in the order shown below at 0.05 significance level.

- 1. Change in NRS score for all subjects
- 2. Change in PCS Total score for all subjects
- 3. Change in NRS score for SCS therapy subjects
- 4. Change in NRS score for DRG therapy subjects
- 5. Change in Promis-29 Pain Interference T-score for all subjects
- 6. Change in Promis-29 Physical Function T-score for all subjects

Change is defined as change in score from baseline to 6 months and is calculated as:

Change in score = Score at Baseline - Score at 6-month

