2.3.2 Descriptive Endpoints

In addition to the above endpoints, data from additional descriptive endpoints or timepoints will be summarized. All analyses will be based on subjects in the Full Analysis Set.

- For NRS, descriptive statistics as defined in section 2.2.1 will be provided at baseline and all scheduled post-baseline visits. Absolute change from baseline summary will also be provided at each scheduled post-baseline visit.
- For Patient reported pain relief, percent change in NRS score from baseline to each scheduled post-baseline visit summary will be provided as defined in section 2.2.1.
- For PROMIS-29, PCS and PVAQ questionnaire data, descriptive statistics as defined in section 2.2.1 will be provided at baseline and all scheduled postbaseline visits. Change from baseline summary will also be provided for each scheduled post baseline visit. All the questionnaire data will be scored according to the scoring manuals prior to data analysis. The weblinks to the scoring manuals are provided in the reference section.
- For Patient and Physician Satisfaction, descriptive statistics as defined in section 2.2.2 will be provided for each satisfaction category.
- For all Pain condition related medications, descriptive statistics as defined in section 2.2.2 will be provided for in Full Analysis Set
 - Subjects who took pain medication at baseline and stopped post-baseline
 - Subjects who did not take pain medication at baseline but started post-baseline
 - o Subjects who increased dose from baseline to each post-baseline visit
 - o Subjects who decreased dose from baseline to each post-baseline visit

For pain condition related medication usage, the total morphine milligram equivalent (MME) dosage will also be calculated for each patient. The weblink for MME calculation is provided in the reference section of this SAP. Descriptive statistics as described in section 2.2.1 will be provided for total MME.

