3.5 Additional Data

For PCS Total score, change from baseline to 6 months will be reported for subjects in Full Analysis Set, who are catastrophizing at baseline (PCS Total score at baseline >=30).

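### Does using one subtraction order (baseline minus 6-month) for all six tested endpoints misread Physical Function, where a higher score is better?

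*SAP*

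**What the plan says.** SAP 2.3.1 names six endpoints for successive evaluation at the 0.05 level. They are NRS change in all subjects, PCS Total change, NRS change in the SCS and DRG therapy groups separately, PROMIS-29 Pain Interference change and, last, "Change in Promis-29 Physical Function T-score for all subjects". One definition follows the list and covers the 6-month change: "Change in score = Score at Baseline - Score at 6-month".

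Protocol 6.5.1 fixes the direction of the PROMIS-29 scales: "Greater scores represent more of whatever concept is being measured (e.g., depression or physical function"). The instrument "covers 7 health domains (depression, anxiety, physical function, pain interference, fatigue, sleep disturbance, and social function) with 4 questions each". Protocol 6.5.2 describes the PCS as a measure of negative thoughts about pain, so a higher score is worse. The NRS measures pain intensity.

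SAP 2.3.2 adds descriptive summaries. For PROMIS-29, PCS and PVAQ: "Change from baseline summary will also be provided for each scheduled post baseline visit". For NRS: "Absolute change from baseline summary will also be provided at each scheduled post-baseline visit". Neither sentence restates a subtraction order. SAP 3.5 adds a PCS Total summary in subjects who are catastrophizing at baseline, where "change from baseline to 6 months will be reported for subjects in Full Analysis Set".

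The public copy does not show everything. A figure is missing from SAP 2.3.1. SAP 2.4, 2.7, 2.10 and 7.0 appear as headings only. SAP 2.2.1 refers to table mockups that are not included.

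**The concern.** A reader who sees positive values for improvement in five rows will expect the sixth to work the same way, and it does not. A real gain in physical function is reported as a negative number. Improving quality of life is one of the study objectives, and Physical Function is one of only two PROMIS-29 domains formally tested, so a misread sign there would matter.

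There are two further worries. First, change from baseline is commonly programmed as visit value minus baseline. If SAP 2.3.2 were programmed that way, the 6-month change in NRS, PCS Total, Pain Interference and Physical Function would appear with one sign in the tested-endpoint table and the opposite sign in the descriptive table. Second, the visible text gives no sidedness. If a single one-sided rule of change above zero were applied down the whole list, endpoint 6 would be tested in the wrong direction.

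**Working it through.** **1. Sign of each endpoint.** The formula is baseline minus 6-month. The score values below are assumed, and each represents an improvement.

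| Endpoint | Baseline | 6 months | Change | Positive means |
|---|---|---|---|---|
| NRS (1, 3, 4) | 7 | 4 | +3 | benefit |
| PCS Total (2) | 30 | 20 | +10 | benefit |
| Pain Interference T (5) | 66 | 60 | +6 | benefit |
| Physical Function T (6) | 35 | 40 | -5 | worse function |

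The observation is correct: endpoint 6 runs the other way.

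**2. Effect on a two-sided test.** Reversing the order multiplies every subject's change by -1. The mean changes sign, the SD does not change, and the absolute t statistic is the same. The documents visible here give no effect size or SD, so assume a gain of 4 points, an SD of change of 8 and 80 evaluable subjects:

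- SE = 8/√80 = 0.894
- half-width = 1.990 × 0.894 = 1.78
- as written: -4.0 (95% CI -5.8 to -2.2)
- reversed: +4.0 (95% CI 2.2 to 5.8)

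The p-value and the conclusion are identical. This follows from symmetry and holds for any other choice of gain, SD or sample size.

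**3. Effect on the sequence.** Physical Function is sixth of six. Whatever its result, no later test is opened or closed by it.

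**4. The case that would do harm.** Take a true improvement of 0.3 SD of change (assumed), the planned 100 subjects and a z-test on the paired change, so that 0.3 × √100 = 3.

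- two-sided 0.05: power 0.85 under either order
- one-sided 0.05 in the beneficial direction (change below zero): Φ(3 - 1.645) = 0.91
- one-sided 0.05 for change above zero: Φ(-3 - 1.645) = 0.000002

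The last line would be a real failure. It requires a uniform one-sided rule that the documents do not state.

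**5. Whether another order would read better in SAP 2.3.2.** Two of the seven PROMIS-29 domains, physical and social function, are better when higher. Protocol 6.4.1 gives five visits: "Follow-up visits will occur in-office at 3, 6, 12, 18, and 24-months". That makes 7 × 5 = 35 domain-by-visit change summaries.

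- baseline minus visit: positive means worse in 2 × 5 = 10 of 35 (29%)
- visit minus baseline: positive means worse in 5 × 5 = 25 of 35 (71%)

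No single order makes every PROMIS-29 row read the same way. Mixed directions come with the instrument, and any analyst tabulating it has to label them.

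**6. Whether SAP 3.5 is undefined.** SAP 2.3.1 defines the change from baseline to 6 months, and SAP 3.5 reports PCS Total over that same interval. The definition carries over.

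**The case for a change.** The best argument for acting is that it costs almost nothing. One sentence naming the favourable direction per endpoint, and another extending the subtraction order to SAP 2.3.2, would remove any doubt before the tables are programmed. The facts behind that argument stand. The sign does reverse for endpoint 6. The formula is tied to 6 months, while SAP 2.3.2 covers every scheduled visit, so its order there is inferred and not stated.

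The rest is weaker. SAP 2.3.1 and 2.3.2 both sit under the endpoint analysis heading, and the second is presented as an addition to the first. Contradictory tables would need a programmer to set aside the only convention that is written down. The two table worries also exclude each other. The 10-of-35 count applies only if the order carries into SAP 2.3.2, and the opposite-sign problem arises only if it does not. Direction labels and footnotes usually belong in table shells. Those shells exist according to SAP 2.2.1 but cannot be seen here, so nobody working from the public copy can say that the labels are absent. Finally, redefining Physical Function alone as 6-month minus baseline would give the word change two meanings within one list, which is worse than the present uniform rule.

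**Conclusion.** The observation is accurate, but no change to the plan is needed. A uniform raw difference is a legitimate convention. The subtraction order is explicit for the tested endpoints, and Protocol 6.5.1 tells the reader which way Physical Function runs. Under a two-sided test the effect on p-values, power and conclusions is zero, and no other endpoint depends on endpoint 6. What remains is the printed sign of one tested estimate and its interval, and of up to 10 of 35 descriptive PROMIS-29 summaries if the same order is used throughout. Routine table labelling deals with that. A note on direction would be a reasonable editorial courtesy, but it would alter no analysis.

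This rests on two assumptions: that the tests are two-sided, or one-sided in the beneficial direction for each endpoint, and that SAP 2.3.2 is programmed with the order in SAP 2.3.1. The first is not confirmed in the visible text, although the missing figure and the blank SAP sections may state it. If a uniform one-sided test of change above zero were found there, the conclusion for endpoint 6 would have to be revisited.

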2.3.2 Descriptive Endpoints

In addition to the above endpoints, data from additional descriptive endpoints or timepoints will be summarized. All analyses will be based on subjects in the Full Analysis Set.

- For NRS, descriptive statistics as defined in section 2.2.1 will be provided at baseline and all scheduled post-baseline visits. Absolute change from baseline summary will also be provided at each scheduled post-baseline visit.
- For Patient reported pain relief, percent change in NRS score from baseline to each scheduled post-baseline visit summary will be provided as defined in section 2.2.1.
- For PROMIS-29, PCS and PVAQ questionnaire data, descriptive statistics as defined in section 2.2.1 will be provided at baseline and all scheduled postbaseline visits. Change from baseline summary will also be provided for each scheduled post baseline visit. All the questionnaire data will be scored according to the scoring manuals prior to data analysis. The weblinks to the scoring manuals are provided in the reference section.
- For Patient and Physician Satisfaction, descriptive statistics as defined in section 2.2.2 will be provided for each satisfaction category.
- For all Pain condition related medications, descriptive statistics as defined in section 2.2.2 will be provided for in Full Analysis Set
 - Subjects who took pain medication at baseline and stopped post-baseline
 - Subjects who did not take pain medication at baseline but started post-baseline
 - o Subjects who increased dose from baseline to each post-baseline visit
 - o Subjects who decreased dose from baseline to each post-baseline visit

For pain condition related medication usage, the total morphine milligram equivalent (MME) dosage will also be calculated for each patient. The weblink for MME calculation is provided in the reference section of this SAP. Descriptive statistics as described in section 2.2.1 will be provided for total MME.

2.4 Sample Size Calculations

2.5 Interim Analysis

2.6 Timing of Analysis

The final analysis will take place once all subjects have exited the study.

2.7 Study/Trial Success

2.8 Subgroups for Analysis

Subgroup analysis using variables such as therapy (DRG vs SCS), salvage method and manufacturer type may be performed as needed for exploratory purposes.

2.9 Poolability Issue

No poolability analysis is planned for the study.

2.10 Multiplicity Issues

2.11 Adjustments for Covariates

Unless otherwise specified, no adjustments for covariates will be made for any of the variables in the analyses.

2.12 Exploratory Analysis

Exploratory Analysis may be performed as appropriate per study teams' decision.

3.0 DESCRIPTIVE ENDPOINTS AND ADDITIONAL DATA

The following data will be summarized descriptively as outlined in Section 2.2 Statistical Methods in the SAP.

3.1 Baseline and Demographic Characteristics

The following baseline and demographic variables will be summarized for all subjects in the Full Analysis Set: age, gender, ethnicity, race, BMI, impact of pain, activity level, work status, etc. De-registered subjects will not be included in this summary.

3.2 Adverse Events

All adverse events related or unrelated to the device, serious and non-serious will be summarized for all subjects in the Full Analysis Set using the number of events, the number of subjects with event(s), and the percentage of subjects with event(s). All CEC adjudicated adverse events will also be summarized for all subjects in the Full Analysis Set with the number of events, the number of subjects with event(s), and the percentage of subjects with events.

3.3 **Subject Early Termination**

Subject early termination reasons including deaths, withdrawals, lost-to-follow-up, etc. will be summarized for subjects in the Full Analysis Set. A listing will also be provided for subjects who deregistered from the study with reasons for de-registration.

3.4 **Protocol Deviation**

Protocol deviations will be summarized descriptively by category for subjects in the Full Analysis Set in whom a protocol deviation was reported.

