5.5 Subject Deregistration

Subjects are considered deregistered if a study device was not introduced to the subject for any reason (e.g., payor denial or inability to place leads), and are excluded from the analysis set.

The Full Analysis Set (FAS) is the analysis set which is as complete as possible and as close as possible to the intention-to-treat ideal of including all enrolled subjects. Deregistered subjects will be excluded from the FAS, but must be followed and documented according to the CIP requirements until they withdraw informed consent.

Subjects who are deregistered or discontinued for the above-mentioned reasons will not count towards the total sample size.

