7.3 Adverse Event and Device Deficiency/Device Malfunction Reporting

7.3.1 Adverse Event Reporting

Safety surveillance and reporting starts as soon as the patient is enrolled in the clinical investigation. Safety surveillance and reporting will continue until the last follow-up visit has been performed, the subject is deceased, the subject concludes participation in the clinical investigation, or the subject withdraws from the clinical investigation. All adverse event data, including deaths and device deficiency data (if applicable), will be collected throughout the time period defined above and will be reported to the Sponsor on a CRF. Additional information with regard to an adverse event should be updated within the appropriate CRF.

Unchanged, chronic, non-worsening, or pre-existing conditions are not AEs and should not be reported.

An offline form will be made available to allow the Investigator to report SAEs in the event the entry cannot be made in the EDC. This does not replace the EDC reporting system. All information must still be entered in the EDC system as soon as feasible.

SAE Reporting

The Investigator should report all SAEs to the Sponsor as soon as possible but no later than outlined below.

Clinical Site	Reporting timelines
All Sites	SAEs must be reported to the Sponsor no later than 3 calendar days from the day the site personnel became aware of the event or as per the investigative site's local requirements, if the requirement is more stringent than those outlined.

The date the site staff became aware the event met the criteria of an SAE must be recorded in the source document. The Investigator will further report the SAE to the local IRB/EC according to the institution's IRB/EC reporting requirements.

Reportable events to sponsor are considered:

- 1. All serious adverse events regardless of relatedness to the device and/or procedure
- 2. All device/procedure related adverse events

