8.1 Analysis Populations

The Full Analysis Set (as defined in Section 5.5) will be the analysis population.

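### Adverse events are summarised only in the Full Analysis Set, so events in subjects with an attempted placement but no device introduced reach no described safety output

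*SAP*

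**What the plan says.** **Who is removed.** Protocol 5.5 treats a subject as deregistered if "a study device was not introduced to the subject for any reason (e.g., payor denial or inability to place leads"). It continues: "Deregistered subjects will be excluded from the FAS, but must be followed and documented according to the CIP requirements", until consent is withdrawn. These subjects also do not count towards the sample size of 100.

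**Which population is analysed.** Protocol 8.1: "The Full Analysis Set (as defined in Section 5.5) will be the analysis population". Neither document describes a safety set or an all-enrolled set.

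**What is collected.** Protocol 7.3.1: "Safety surveillance and reporting starts as soon as the patient is enrolled in the clinical investigation". Under the same section all serious events, and all events related to the device or procedure, are reportable to the sponsor. Protocol 3.2 sends serious device- or procedure-related events to the Clinical Events Committee (CEC).

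**What is reported.** SAP 3.2: "All adverse events related or unrelated to the device, serious and non-serious will be summarized for all subjects in the Full Analysis Set", and "All CEC adjudicated adverse events will also be summarized for all subjects in the Full Analysis Set". SAP 3.3 summarises early terminations, deaths included, in the same set and adds: "A listing will also be provided for subjects who deregistered from the study with reasons for de-registration".

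**The concern.** The subjects left out are not all administrative losses. Payor denial happens before anything is done to the subject. Inability to place leads implies that a procedure was begun. If it caused harm and was abandoned, the subject is deregistered and the harm leaves both the numerator and the denominator. Exclusion can then depend on the outcome being measured, and the serious and procedure-related percentages may be biased downward.

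In a study of about 100 subjects a single serious event moves a percentage by about one point, and an individual event may matter in its own right. A reader of the final safety tables could not tell that such events had occurred, although the sponsor holds them.

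**Working it through.** The plan states no figure to reproduce. The check is a trace of where an event in a failed placement would go, followed by an illustration of size.

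**Trace**

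| Step | Source | Event in a subject with a failed placement and no device introduced |
|---|---|---|
| Collected? | Protocol 7.3.1, 11.4 | Yes: surveillance runs from enrollment, and CRF data are taken for all enrolled subjects |
| Followed up? | Protocol 5.5 | Yes, until consent is withdrawn |
| Adjudicated? | Protocol 3.2 | Yes, if serious and device- or procedure-related |
| In the Full Analysis Set? | Protocol 5.5, 8.1 | No |
| In the all-event summary? | SAP 3.2 | No |
| In the CEC-adjudicated summary? | SAP 3.2 | No |
| In the early termination and death summary? | SAP 3.3 | No |
| In the deregistration listing? | SAP 3.3 | The subject and the reason only; the event shows only if it was itself the recorded reason |

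Subjects who had a device introduced during a trial period and later failed permanent placement stay in the Full Analysis Set and are not affected.

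**Illustration of size**

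The documents give neither a failed-placement rate nor an event rate, so every input except the planned 100 subjects is an assumption. Deregistered subjects come on top of the 100, because they do not count towards the sample size.

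- Reported rate: 4 serious procedure-related events in 100 subjects, 4/100 = 4.0%.
- Rate among attempted procedures: (4 + x)/(100 + f), with f failed placements and x events among them.

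| f | x = 0 | x = 1 | x = 2 | x = 3 | Ratio to 4.0% |
|---|---|---|---|---|---|
| 5 | 4/105 = 3.8% | 5/105 = 4.8% | 6/105 = 5.7% | 7/105 = 6.7% | 0.95 to 1.67 |
| 10 | 4/110 = 3.6% | 5/110 = 4.5% | 6/110 = 5.5% | 7/110 = 6.4% | 0.91 to 1.59 |

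The bias can run either way. With no event among the failed placements the reported rate is slightly too high; with one or more it is too low.

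**Why not simply use all enrolled subjects.** Assume a further 20 payor denials and 3 events in 5 failed placements. The all-enrolled rate is 7/(100 + 5 + 20) = 7/125 = 5.6%, against 7/105 = 6.7% among attempted procedures. Subjects who never came to a procedure would dilute the procedural rate.

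**The case against.** Six points can be made for the plan.

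- **Part of the SAP cannot be seen.** Section 2.1.1 has no text in this copy, and the table mockups and appendices are not visible. SAP 3.1 also says separately that deregistered subjects are left out of its summary, which would be redundant if the SAP's Full Analysis Set always excluded them. This stands as a limit: an unseen listing cannot be ruled out. It does not displace protocol 5.5, which protocol 8.1 cites as the definition and with which SAP 3.1 and 3.3 agree.
- **The group is narrow.** Reprogramming, or connecting a generator to existing leads, needs no new lead placement. The word *introduced* is also undefined, so a lead inserted and withdrawn might keep the subject in the set. That could shrink the group considerably. The protocol nevertheless classes inability to place leads as not introduced, and the ambiguity itself needs settling.
- **Harm as the cause of exclusion is inferred.** Correct: the documents do not say that failed placements are harmful. The rule applies whatever the reason, so it allows the case without showing that it is common.
- **The upper figure is extreme.** Three serious events in 5 failed placements is a 60% rate. At the same 4% assumed for the analysed subjects, 5 failed placements would yield 5 × 0.04 = 0.2 expected events and essentially no bias. This stands; the range shows what is possible, not what is likely.
- **Safety is descriptive here and surveillance is intact.** The study is a single-arm post-market study of marketed devices with no safety hypothesis. Collection, sponsor reporting and adjudication are unaffected. This bounds the consequence but does not remove it: the final tables would still omit events the study holds.
- **A listing alone would do.** It would make the events visible but leave the percentages without the failed attempts. It is a reasonable fallback.

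**Conclusion.** The concern holds and should be fixed. Applied as written, the population rule leaves collected, and in part adjudicated, events from failed placements out of every adverse event output the available text describes. The fault lies in final reporting, not in subject protection during the study.

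The effect cannot be calculated from the documents. Under the stated assumptions the rate among attempted procedures lies between 0.91 and 1.67 times the reported one, and one omitted event suffices to make the reported rate too low. Confidence is medium. The conclusion rests on protocol 5.5 defining the Full Analysis Set for the SAP, on no relevant listing in the unseen mockups, and on at least some failed placements counting as no device introduced.

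**What to change.** In SAP 3.2:

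1. Define a safety set of all enrolled subjects in whom a study procedure (trial, permanent implementation or reprogramming) was started, whether or not a device was introduced. Summarise adverse events, serious adverse events, deaths, device deficiencies and CEC-adjudicated events in it.
2. State how a lead that is inserted and then withdrawn is classified.
3. List any adverse events in the remaining deregistered subjects, such as payor denials, next to the SAP 3.3 listing, so that they are visible without diluting the procedural rates.
4. Keep the Full Analysis Set for effectiveness.

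The cost is one analysis set and one listing. No new event collection is needed. Attempted procedures have to be identified from the recorded deregistration reasons, and whether the CRF captures this cannot be checked in the supplied copy. If it does not, an adverse event listing covering all deregistered subjects is the minimum.

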15.5 Steps Taken to Control or Mitigate Risks

[figure not shown]
The devices used in this study are approved and in commercially distribution. Risks associated with the use of the device under investigation are minimized through device design, Investigator selection and training, pre-specified patient eligibility requirements, and study monitoring to ensure adherence to the

protocol and the use of a DMC. All adverse events and device deficiencies will be reported to the Sponsor and will be monitored internally for safety surveillance purposes.

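### The protocol contradicts itself on which adverse events are collected, and the SAP's all-adverse-event summary rests on the broadest reading

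*SAP*

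**What the plan says.** Four pieces of text bear on the scope of adverse event collection, and they do not agree.

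- **SAP 3.2** sets the analysis: "All adverse events related or unrelated to the device, serious and non-serious will be summarized for all subjects in the Full Analysis Set", as numbers of events and numbers and percentages of subjects.
- **Protocol 7.3.1, first paragraph**, sets a matching rule for collection, with a CRF as the route to the sponsor: "All adverse event data, including deaths and device deficiency data (if applicable), will be collected throughout the time period defined above and will be reported". Section 15.5 repeats it: "All adverse events and device deficiencies will be reported to the Sponsor and will be monitored internally for safety surveillance purposes".
- **Protocol 7.3.1, closing list**, is narrower. Under the lead-in "Reportable events to sponsor are considered" it has two items: "All serious adverse events regardless of relatedness to the device and/or procedure" and "All device/procedure related adverse events".
- **The visit lists** (6.2.2 trial implementation, 6.2.3 end of trial, 6.3 permanent implementation, 6.4.1 follow-up) are narrower still. Each has an item worded "Device-related adverse events (if applicable" and an item for serious events, and no other adverse event item.

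The definition in 7.1.1 counts an event as adverse whether or not the device is involved, so the term itself does not exclude unrelated events.

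**The concern.** A table of all adverse events is only as complete as the collection rule behind it. Here a site could follow the first paragraph of 7.3.1 and record everything, follow the closing list and leave out non-serious unrelated events, or work from the visit list and also leave out non-serious events caused by the procedure but not by the device. With up to 40 sites, the overall percentage could partly reflect which sentence each site used, and nobody reading the table could tell.

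The procedure-related gap matters separately. Implementation can mean a new pulse generator on existing leads or a full system replacement (protocol 1.1.2), so some subjects will have surgery. The closing list in 7.3.1 makes non-serious procedure-related events reportable, yet no visit list prompts for them. Protocol 7.2 describes the investigator's assessment of device relationship only, and SAP 3.2 names relation to the device only.

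SAP 4.1 mentions only added hypothesis testing as a change from the protocol, so nothing there alerts a reader to a question about adverse event scope.

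**Working it through.** The documents give no adverse event rate, so there is no figure to reproduce. The check is a side-by-side reading of what each text covers.

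| Kind of event | 7.3.1 first paragraph and 15.5 | 7.3.1 closing list | Visit lists | SAP 3.2 |
|---|---|---|---|---|
| Serious, any relation | yes | yes | yes | yes |
| Non-serious, device-related | yes | yes | yes | yes |
| Non-serious, procedure-related only | yes | yes | no | yes, but no category of its own |
| Non-serious, unrelated to either | yes | no | no | yes |

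Three things follow.

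1. The protocol states three different scopes, each nested in the one before. The SAP matches the widest.
2. Serious events and non-serious device-related events are covered by every text, so the contradiction does not touch those summaries.
3. The two lower rows are exposed. The fourth depends on whether a site follows the first paragraph or the closing list. The third depends on whether it works from 7.3.1 or from the visit list.

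**Scale of the possible effect on the percentage of subjects with any event.** A subject with a recorded serious or related event is already counted, whatever else goes unrecorded. The percentage therefore falls only for subjects none of whose events are recorded:

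shortfall in percentage points = 100 × m / N,

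where m is the number of subjects whose only events are non-serious, unrelated and unrecorded, and N is the size of the Full Analysis Set. Taking N = 100 from the planned sample size in protocol 5.7 (assumed fully achieved), each such subject costs 100 × 1 / 100 = 1 point. The documents give no basis for m. If every site follows the first paragraph of 7.3.1, m = 0 from this cause and the shortfall is 0. The count of events is more exposed than the percentage, because every unrecorded event reduces it.

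**The case against.** The strongest reply is that the protocol does contain the broad rule, twice, and that the SAP is consistent with it. The closing list in 7.3.1 follows the SAE Reporting subheading, its three-day timeline and the sentence on informing the IRB/EC, so it can be read as part of that reporting rule and not as a limit on collection. The visit lists do not cancel a surveillance rule that runs continuously from enrollment. The summary is descriptive, and no hypothesis test depends on it.

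Much of this stands, and it rules out some stronger readings that a reader might infer:

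- *That only serious and related events are reportable.* The first paragraph of 7.3.1 and section 15.5 say otherwise.
- *That sites are told to withhold non-serious unrelated events.* No sentence does so. The one instruction in 7.3.1 not to report concerns unchanged, chronic, non-worsening or pre-existing conditions.
- *That the overall rate is bound to be an undercount.* This holds only if some sites use the narrower text.
- *That an incomplete rate will be published.* SAP 3.2 speaks only of a summary.

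The reply does not remove the contradiction. The second item of the closing list is not confined to serious events, so the list is hard to read as a rule for serious events alone. That reading also leaves the four visit lists unexplained. The case report forms and the schedule of events might settle the matter, but their content is not in the supplied text. That absence is no fault of the plan.

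**Conclusion.** The concern holds as an internal contradiction in a collection rule, with a conditional consequence for one descriptive table. If sites differ in the text they follow, non-serious unrelated events may be captured unevenly and the all-adverse-event percentage may be an undercount of unknown size. It is zero if every site follows the broad text.

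Non-serious procedure-related events are reportable under either part of 7.3.1 but have no prompt in any visit list. That mismatch remains however the wider question is settled.

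The conclusion rests on the wording alone. It assumes that sites could reasonably act on either the visit lists or the closing list, and that the unseen forms do not already impose one scope. The point merits correction because minor events missed during 24 months of follow-up cannot be reliably recovered at the end.

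**What to change.** Bring protocol 6.2.2, 6.2.3, 6.3, 6.4.1, 7.3.1 and 15.5 and SAP 3.2 to one scope.

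In either case, change the visit-list item to *Device- or procedure-related adverse events*, so that it agrees with the closing list in 7.3.1. Then choose one of two routes:

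- **(a) Broad.** State that all adverse events are collected, add them to the closing list in 7.3.1 and to the visit lists, and keep SAP 3.2 as it is.
- **(b) Narrow.** Limit and label the SAP 3.2 tables as all serious adverse events plus all device- or procedure-related adverse events, and amend both the first paragraph of 7.3.1 and section 15.5. If 15.5 is left alone, the contradiction survives.

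If data were already collected under the mixed text, label the table by what was reportable and do not present the non-serious unrelated category as complete.

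The cost is a wording amendment to the protocol and, under (b), to the SAP, which then has a narrower adverse event table. Under (a), any site that had worked from the narrower text would have more to record. Whether a form also needs changing cannot be judged from the supplied text.
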